Experts recommend a series of services and resources for a good functional recovery of patients who have suffered a stroke. Among other issues are training and health education programs. In this way, the nursing profession is trained to formulate personalized comprehensive care plans, promote comprehensive recovery, and strengthen communication with patients and their families. Nurses should perform interventions in accordance with general practice to provide continuity of care for stroke patients throughout the patient's recovery journey. Integrated care is desirable and constitutes a reference model for all situations considered. Planning for teaching and discharge from hospital can help families of patients who have suffered a stroke to make specific long-term arrangements for the expected functional outcome. In addition, post-discharge follow-up and support interventions should be implemented that are individualized to the caregiver's needs. Early rehabilitation intervention and evidence-based nursing interventions showed significant improvements in their scores on tests related to cognitive impairment and neurological deficit, as well as improved disability. However, there are hardly any standardized, approved and scientifically proven health education programs. The application of nursing interventions, through health education, to minimize the levels of depression caused by the disease, to two groups, case and control, will allow us to evaluate the influence of health education on the symptomatology of depression and improve the quality of life in patients who have suffered an ischemic stroke.

Study hypothesis

A nursing intervention based on health education will improve quality of life and reduce the symptoms of depression in patients who have suffered an ischemic stroke.

Objectives

General objective: to determine the effect of a nursing intervention based on health education on quality of life and depression symptoms in people who have suffered an ischemic stroke.

Specific objectives:

1. To assess and compare the level of depression in patients who have suffered an ischemic stroke.
2. To assess and compare the degree of autonomy and level of functional dependence of patients who have suffered an ischemic stroke.
3. To assess and compare the cognitive status of patients who have suffered an ischemic stroke.
4. To assess and compare neurological deficits of patients who have suffered an ischemic stroke.

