According to the Atlas of Stroke in Galicia published by the Spanish Society of Neurology in 2018, the autonomous community of Galicia had a population of 2,701,819 inhabitants. Applying an incidence rate of 187.4 cases per 100,000 inhabitants, according to the IBERICTUS study, 5,064 new cases of stroke are estimated each year in Galicia per 100,000 inhabitants. The province of Lugo has 324,842 inhabitants on 1 January 2024, according to the INE, which, applying the same incidence rate, estimates 609 new cases of stroke per 100,000 inhabitants per year. Considering the proportion of ischemic strokes compared to other types of strokes 80:20, the estimated cases of the same would be 487 new cases in Lugo.

In relation to the calculation of the sample size, the following formula is applied.

$$n = \frac{\left[Z_{1-\frac{\alpha}{2}} \sqrt{2p(1-p)} + Z_{1-\beta} \sqrt{p_1(1-p_1) + p_2(1-p_2)} \right]^2}{(p_1 - p_2)^2}$$

Where:

- P2 (frequency of exposure between controls) = 0.4
- OR=4
- Assuming a 1:1 ratio of controls per case
- n = participants as the minimum sample size.

Assuming the calculations, the representative sample size of stroke patients in the province of Lugo would be 70 patients, 35 patients receiving the intervention and 35 controls.

Primary and secondary variables

Independent variables:

- Socioepidemiological: sex, age (< 65 years, 65-80 years, >80 years), date of ischemic event.
- Clinical Signs: type of stroke, treatment modality (received rt-PA or mechanical thrombectomy according to the candidates' protocol), number of falls, degree of pain, presence of pressure ulcers, genesis of new pressure ulcers, episodes of bronchoaspiration, presence of pneumonia, presence of dysphagia, vital signs (blood pressure, glycemia, temperature).
- You receive health education after a stroke or do not receive health education after a stroke.

Dependent variables:

- Assessment of cognitive status by scoring the Mini Mental State Examination (MMSE) questionnaire.
- Assessment of depression symptomatology by scoring on the Beck questionnaire (BDI) or also called depression self-report inventory.
- Assessment of autonomy and ability to perform in basic activities of daily living by means of a score from the Barthel Index.
- Neurological deficit using the NIHSS scale.
- Assessment of quality of life by scoring on the European Quality of Life Scale.

Instruments

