This section lists the instruments that will be used to measure the variables under study. They are described in a more extensive manner in Annex I.

1. Mini mental status examination (MMSE).
2. Beck Questionnaire (BDI).
3. Barthel index.
4. National institute of Health Stroke Scale (NIHSS).
5. Visual Analog Scale (VAS)
6. European Quality of Life Scale (EQLS).

Description of the intervention

The initial evaluation of the patients will be carried out for the collection of the variables to be studied upon admission. Subsequently, 2 groups will be established: the group to which a health education program will be applied (intervention of this study that will be specified below) and the control group. Finally, a follow-up is proposed at 3 and 6 months after the health education intervention to collect data related to the chronic/stabilization phase in post-stroke recovery.

Nursing intervention: Health education for post-stroke patients

Objectives

- Learn to identify and recognize prodromal symptoms of a new ischemic event.

- Identify what changes have occurred or may occur in patients after the sequelae of the ischemic event and how they may impact their daily lives.
- Describe the recommended care that patients can incorporate into their daily lives to reduce the impact of sequelae and improve their quality of life.
- Learn to recognize and manage early signs and symptoms of low mood and depressive symptoms.

Methodology

The sessions taught are based on meaningful learning, also supported by constructivist, cognitivist and behavioural learning.

The program consists of 3 fundamental pillars: session 1. *Early symptoms of stroke and recognition*, session 2. *Living with stroke: the day-to-day care*, session 3. *Mood management*. In addition, a workshop (session 4) will be designed for intervention in depression based on the development of coping tools through full breathing techniques, relaxation techniques, psychotherapy and mindfulness. All sessions will preferably be group. The contents of these sessions are detailed in Annex II.

Taking into account that 35 patients will receive the health education program, it is estimated that 3-4 groups of 8-12 people distributed independently in the sessions taught by the same instructor.

Materials

- Classroom for health education at HULA.
- Physical and digital support to support the sessions.

Time scheduling

The sessions will be divided into two different days.

Day 1 (40 minutes)

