The collaborating researchers [name] and [name] will be in charge throughout the research process of the work surrounding it with respect to the contribution to the conception and design of the work, acquisition and analysis of the study data, critical review with important intellectual input, responsibility for the accuracy and completeness of the research, supervision, final approval, and project management.

Statistical analysis plan

A descriptive analysis will be carried out using measures of central tendency, such as mean (M), and dispersion, using standard deviation (SD), to examine quantitative variables. In the case of qualitative variables, absolute frequencies and percentages will be used. To determine the correlation between groups, the Chi-square test (χ^2) will be applied to the qualitative variables. Regarding the quantitative variables, the Kolmogorov-Smirnov test will begin to evaluate the normality of the distribution (n=70). If the quantitative variables show a non-parametric distribution, the Kruskal-Wallis test will be used to compare more than two groups, while the differences between pairs will be analyzed using the Mann-Whitney U test. If they are parametric, it will be appropriate to resort to ANOVA, Tukey and Bonferroni. The association between the variables will be evaluated in terms of strength and direction using Spearman's correlation coefficient. Distracting factors (age and sex) that usually tend to normal will be tested with ANOVA and Levene. The effect of the intervention will be determined using relative risk (RR) Statistical analyses will be performed using PASW Statistics software (version 23.0; SPSS Inc., Chicago, Illinois), establishing a bilateral significance level of $p<0.05$.

Ethical-legal aspects

Compliance with Good Clinical Practice Standards, Declaration of Helsinki, Oviedo

Convention, as well as data protection regulations, management of medical records and other applicable regulations depending on the type of study.

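### The section on primary and secondary variables names no primary, no main visit is set, and one p<0.05 threshold applies with no control across outcomes or visits

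*Protocol*

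**What the plan says.** - **Variables.** Under "Primary and secondary variables" the protocol gives two lists, independent and dependent variables. The dependent list holds five scales without ranking: MMSE, BDI, Barthel Index, NIHSS ("Neurological deficit using the NIHSS scale") and the European Quality of Life Scale.
- **Aim.** The general objective is "to determine the effect of a nursing intervention based on health education on quality of life and depression symptoms". The study hypothesis likewise joins an improvement in quality of life and a reduction in depressive symptoms. Neither is ranked, and no success rule is given.
- **Visits.** Description of the intervention says that "a follow-up is proposed at 3 and 6 months after the health education intervention". Neither visit is named as the main one.
- **Error rate.** The Statistical analysis plan section ends by "establishing a bilateral significance level of" p<0.05. It mentions Tukey and Bonferroni beside ANOVA, as the parametric counterpart of the Kruskal-Wallis and Mann-Whitney comparisons of groups. It also says that the effect of the intervention will be measured by relative risk, without naming the event.
- **Sample size.** The 35 + 35 patients come from a two-proportion formula with P2 = 0.4, described as an exposure frequency, and OR = 4. Neither figure is tied to a listed outcome.

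**The concern.** A heading that announces primary variables over a list that contains none contradicts itself. The choice of a primary variable belongs in a protocol, so a separate analysis plan does not excuse the gap, and this protocol has its own analysis section, which fixes the significance level. No other section fills the gap: the hypothesis names two outcomes, the schedule gives two visits, and the sample size points to no outcome.

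With 70 patients the trial will produce several p-values and have no prior rule for which of them answers its question. A favourable result on one outcome at one visit could be presented as support for the hypothesis, and the stated 0.05 would then not be the error rate of that claim. A choice made after the data are seen cannot be repaired later.

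**Working it through.** **Step 1. Does the sample size reveal the primary?** Inputs from Justification of the sample size: P2 = 0.4, OR = 4, ratio 1:1. Two-sided 0.05 is from the analysis section. Power is not stated; 80% is assumed.

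p1 = OR × P2 / (1 − P2 + OR × P2) = 1.6 / 2.2 = 0.727; mean p = 0.564.

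n = [1.960 × √(2 × 0.564 × 0.436) + 0.842 × √(0.198 + 0.240)]² / (0.727 − 0.4)² = (1.375 + 0.557)² / 0.1071 = 34.8, so 35 per group and 70 in total.

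The stated figure is reproduced, for one test of one binary outcome. All five dependent variables are scores, so the calculation does not identify a primary.

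**Step 2. Does the mention of Bonferroni control the error?** It stands with ANOVA as a follow-up to a comparison of groups. Two arms make one pair, so there is nothing to adjust. Nothing in the section adjusts across outcomes or visits.

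**Step 3. Chance of at least one false positive when there is no effect.** For k independent tests it is 1 − 0.95^k in either direction, and 1 − 0.975^k in the direction of benefit.

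- k = 1: 5% and 2.5%.
- k = 4 (quality of life and depression, two visits): 1 − 0.95⁴ = 18.5%; 1 − 0.975⁴ = 9.6%.
- k = 10 (five scales, two visits): 1 − 0.95¹⁰ = 40.1%; 1 − 0.975¹⁰ = 22.4%.

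The tests will be correlated, and the protocol gives no correlations. The table comes from simulated normal test statistics (400,000 draws), oriented so that positive means benefit, with assumed correlations.

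| Tests | r between outcomes | r between visits | Either direction | Benefit only |
|---|---|---|---|---|
| 4 | 0 | 0.5 | 17.3% | 8.9% |
| 4 | 0.5 | 0.5 | 16.2% | 8.1% |
| 4 | 0.5 | 0.8 | 13.8% | 6.9% |
| 4 | 0.7 | 0.8 | 12.8% | 6.4% |
| 10 | 0.3 | 0.5 | 35.3% | 18.2% |
| 10 | 0.5 | 0.5 | 31.2% | 15.8% |
| 10 | 0.7 | 0.8 | 22.1% | 11.1% |
| 10 | 0.8 | 0.9 | 17.3% | 8.6% |

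**Step 4. What would correction cost instead of ranking?** On the inputs of step 1, Bonferroni over four tests (0.05/4 = 0.0125) leaves 61% power at 35 per group and needs 50 per group for 80%. Over ten tests (0.005) the figures are 48% and 60 per group. Ranking the outcomes avoids this loss.

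**The case against.** Several points against a stronger criticism are sound.

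1. **Direction.** A reader might infer that a false claim of benefit has a chance of 18.5% or 40%. Those figures count results in either direction, including results that favour control, and assume independence. For the two hypothesis outcomes the benefit-direction figure is about 6-10%.
2. **Which tests bear on the hypothesis.** A reader might also infer that any of ten tests could confirm it. It covers only quality of life and depression, so MMSE, Barthel and NIHSS cannot.
3. **The joining word.** The hypothesis links its two outcomes with an *and*. If both had to be significant at one fixed visit, there would be no inflation. But the protocol does not state that rule and does not fix the visit.
4. **Emphasis on depression.** Specific objectives 7 and 8 concern depression, and objective 8 is the one that expressly compares those who received the education with those who did not. If the BDI alone were primary, two visits would give at most 1 − 0.95² = 9.75% two-sided and 1 − 0.975² = 4.9% in the direction of benefit. This supports choosing the BDI, but the protocol does not make that choice.
5. **What is tested when.** The protocol does not say that every scale is compared at each visit. The follow-up text lists no scales, and the Annex III collection table has no 3- or 6-month columns. The ten-test case is an inference.

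These points reduce the size of the problem. They do not supply a primary variable, a main visit or a success rule.

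**Conclusion.** The concern holds in a limited form. The protocol promises primary variables and names none, sets no main visit, gives no rule for its two-part hypothesis, and applies one two-sided 0.05 without control across outcomes or visits.

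If either hypothesis outcome at either visit may be taken as support, the chance of at least one false positive is about 13-19% two-sided, or about 6-10% in the direction of benefit against a nominal 2.5%. If all five scales were tested at both visits, the ranges would be about 17-40% and 9-22%, but that schedule is inferred and three of the scales do not bear on the hypothesis. The upper ends assume independence; the lower ends rest on assumed correlations. The documents do not support the reading that a false claim of benefit has a 40% chance.

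**What to change.** - **Rank the outcomes.** Name one primary variable and one visit, for example the BDI at 6 months, which agrees with specific objectives 7 and 8. Test it at two-sided 0.05.
- **State the success rule.** Test quality of life at the same visit at 0.05 only if the first test is significant. Alternatively, state that both must be significant.
- **Label the rest.** Make the other visit and MMSE, Barthel and NIHSS secondary, reported as estimates with 95% confidence intervals and no confirmatory claim.
- **Match the effect measure and sample size.** The present basis compares two proportions and the effect is a relative risk. Either define the primary as binary, for example using the cut-off of 14 on the BDI given in Annex I, or restate the basis and effect measure for a score. If binary, write down the event and its direction: OR = 4 raises the proportion from 0.400 to 0.727, which describes a favourable event such as a BDI below 14.

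**Cost.** With the fixed sequence, the second outcome can be claimed only if the first succeeds; requiring both makes success harder. The sample-size justification must be restated, so this is more than a change of wording. No extra patients are proposed, but whether 35 per group suits the chosen primary can be judged only after that restatement.

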5. Assess and compare the risk of bronchoaspiration, the presence of pressure ulcers, swallowing, blood pressure, temperature and glucose level and assess the level of pain.
6. To correlate the cognitive state and the level of depression symptomatology with implemented variables.
7. To reduce the psychological impact of depression in patients who have suffered an ischemic stroke who have received health education.
8. To compare the level of depression symptoms in patients who have suffered an ischemic stroke who received health education with those who did not.

Type of study

It is a quasi-experimental, longitudinal and prospective clinical trial.

Material and methods

Scope of study

For the preparation of this study, the target population was patients who have suffered an ischemic stroke for the first time and were treated by physicians from the Neurology and Neurosurgery Service of the Lucus Augusti University Hospital (HULA).

Definition of the subjects to be studied

A representative sample size of patients who have suffered an ischemic stroke for the first time and treated by physicians from the Neurology and Neurosurgery Service of the HULA will be collected. From this sample, 2 groups will be extracted: the group to which a health education program will be applied and the control group to which this program will not be applied.

Subject selection and withdrawal

Inclusion criteria: anterior or posterior cerebral occlusion, age ≥ 18 years.

Exclusion criteria: intracranial hemorrhage, pregnancy, cognitive inability to participate, non-acceptance to participate in the study and administer questionnaires.

Recruitment and recruitment of participants

Prior to the recruitment process, the required informed consent signed by said participant will be obtained. Next, the variables will be collected. The recruitment of participants will be carried out by the principal investigator and collaborating researchers of the study in the neurology and neurosurgery ward:

- [name]
- [name]
- [name]
- [name]

The tasks "*Bibliographic Review, Study Design, Documentation Presentation, Database Design*" will be carried out by the collaborating researcher [name] supervised and in collaboration with the collaborating researchers [name] and [name].

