- Session 1: Early symptoms of stroke and recognition of these.
- Session 2: Living with stroke: the day-to-day care.

Day 2 (40 minutes)

- Session 3: Mood management and depression.
- Session 4: relaxation workshop with guided meditation (mindfulness)

Timeline and expected completion date.

Once the Santiago-Lugo Research Ethics Committee issues this research plan as favorable, the study will begin following the following schedule:

Task	July and August 2025	September 2025 to November 2025	November 2025 to May 2026	June to August 2026	September 2026 to January 2027	February to December 2027	January 2028 to September 2028
Literature review							
Study design							
Submission of documentation							

Database design							
Patient recruitment and immediate data							
Conducting the workshops							
Follow-up 3 months							
Follow-up 6 months							
Data integration and statistical analysis							
Results, discussion, conclusions							
Scientific dissemination							

The tasks "*BibliographicReview, Study Design, Presentation of Documentation, Database Design*" will be carried out by the collaborating researcher [name].

The recruitment of patients and immediate data will be carried out consecutively on the neurology and neurosurgery floor of the HULA by the collaborating researchers [name], [name], [name] and the principal investigator [name] and by the collaborating researcher in consultation of the neurology of the HULA [name].

The performance of the sessions is conditioned by the time of diagnosis of the stroke. In this way, it is necessary to recruit a minimum group of patients to carry out the workshops according to the established methodology. Subsequently, these will be carried out by the collaborating researcher [name]. After 3 and 6 months following the workshops, the same researcher together with the collaborating researcher [name] will carry out the follow-up and reevaluation in the neurology consultation of the HULA.

Finally, the process of integrating data and statistical analysis together with the final task of writing results, discussion and conclusions and their dissemination will be carried out by the collaborating researcher [name].

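### The trial follows the same patients over three visits, but the plan names only independent-groups tests and no method for change within patients

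*Protocol*

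**What the plan says.** The Type of study section states: "It is a quasi-experimental, longitudinal and prospective clinical trial". Description of the intervention sets the measurement times: "The initial evaluation of the patients will be carried out for the collection of the variables to be studied upon admission", and later "a follow-up is proposed at 3 and 6 months after the health education intervention". The recruitment section and the timeline confirm that these are return visits, at which the researchers "will carry out the follow-up and reevaluation in the neurology consultation of the HULA". The Annex III notebook also has several in-hospital columns per participant for the BDI and the MMSE.

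There are two arms; the sample-size section says the sample "would be 70 patients, 35 patients receiving the intervention and 35 controls".

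The Statistical analysis plan section then fixes the tests:
- For qualitative variables: "To determine the correlation between groups, the Chi-square test".
- For non-normal quantitative variables: "Kruskal-Wallis test will be used to compare more than two groups, while the differences between pairs will be analyzed using the Mann-Whitney" U test.
- For normal quantitative variables: ANOVA with Tukey and Bonferroni.
- Spearman for association, ANOVA and Levene for age and sex, and a relative risk for the effect of the intervention.

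The section names no signed-rank, Friedman or McNemar test, repeated-measures ANOVA, mixed model or GEE. It defines no change score or analysis visit and gives the admission score no role.

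Objective 7 reads: "To reduce the psychological impact of depression in patients who have suffered an ischemic stroke who have received health education". Objective 8, separately, compares depression symptoms between those who did and did not receive the education.

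**The concern.** A patient's admission, 3-month and 6-month scores are correlated. The named group tests treat every score as coming from a different person. Used on two visits of the same patients, they overstate the variance of the difference, so p-values are too large and real change is missed.

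Objective 7 is worded about the educated patients alone. If it is tested as a before-after change, the listed methods offer no suitable test. Even with the right test, a fall within one arm could not be credited to the education, because nothing in that comparison removes the recovery that would have happened anyway.

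The gap cannot simply be put down to detail awaiting a later document: the protocol has its own analysis section, and that section chooses the tests.

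**Working it through.** **Inputs from the protocol.** Two arms of 35; three measurement times; two-sided 5% level; P2 = 0.4 and OR = 4.

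**Assumptions.** The within-patient correlation ρ is not given; 0.3 to 0.7 is shown. Scores are taken as normal with equal variance at each visit. The size of change over time is also not given; 0.4 and 0.5 SD are used.

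**The plan's own figure.** p1 = 4 × 0.4 / (0.6 + 4 × 0.4) = 1.6 / 2.2 = 0.727, and the mean proportion is 0.564. With 80% power (not stated, assumed):

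n = [1.96 × √(2 × 0.564 × 0.436) + 0.842 × √(0.198 + 0.240)]² / 0.327² = (1.375 + 0.557)² / 0.107 ≈ 34.8, so 35 per arm and 70 in total.

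The stated size is reproduced. It rests on one comparison of two proportions, one value per patient, so the point below does not alter it.

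**Two visits of the same patients.** The independent-groups test assumes a variance of 2σ²/n for the difference. The true variance is 2σ²(1 − ρ)/n. The true size is therefore 2[1 − Φ(1.96/√(1 − ρ))].

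| ρ | True size at nominal 5% |
|---|---|
| 0.3 | 1.9% |
| 0.5 | 0.6% |
| 0.7 | 0.03% |

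Simulation of Mann-Whitney agrees: about 2% at ρ = 0.3, 0.6% at 0.5, and close to zero at 0.7. Kruskal-Wallis across the three visits of one arm behaves the same way (1.6%, 0.6%, below 0.1%). Friedman returns to 4.9%, 4.6% and 5.2%.

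**Power for a change over time, n = 35.** With d the change in SD units:
- unpaired ≈ Φ[(d − 1.96√(2/n)) / √(2(1 − ρ)/n)]
- paired ≈ Φ[d / √(2(1 − ρ)/n) − 1.96]

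For d = 0.4, 1.96√(2/35) = 0.468.
- ρ = 0.5: the standard error is 0.169. Unpaired Φ(−0.41) = 34%; paired Φ(0.41) = 66%.
- ρ = 0.7: the standard error is 0.131. Unpaired Φ(−0.52) = 30%; paired Φ(1.10) = 86%.

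Simulating the rank tests themselves gives about 30% for Mann-Whitney throughout, and 61%, 71% and 82% for signed-rank at ρ = 0.5, 0.6 and 0.7. For d = 0.5 the approximation gives 56%, 57% and 60% unpaired against 71%, 84% and 97% paired, at ρ = 0.3, 0.5 and 0.7.

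**Arm against arm, one visit.** Simulated size of Mann-Whitney: 4.8%, 4.8% and 5.1% at ρ = 0.3, 0.5 and 0.7. Mann-Whitney on each patient's change: 4.6%, 5.4% and 4.9%. Both are sound.

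**The case against.** The strongest reply is that the trial's main question, education against no education, is answered by comparing the arms. Mann-Whitney or chi-square at one visit does that correctly. This stands: objective 8 can be tested validly as written, and it would be wrong to infer that all the planned p-values are faulty.

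Three other readings are tempting and go too far.

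- *That follow-up visits will be pooled.* Entering the 3- and 6-month scores as separate observations would raise the false-positive rate of the arm comparison to 2[1 − Φ(1.96/√(1 + ρ))], about 11% to 15% by simulation for ρ = 0.5 to 0.8. But the protocol nowhere says it will pool, and its normality check refers to n = 70, which is one value per patient. The inflation would arise only if visits were pooled.
- *That Kruskal-Wallis must be meant for the three visits, because there are only two arms.* The variables section lists age in three bands and type of stroke, and the test could serve either. No sentence assigns it to time points.
- *That objective 7 is certainly a before-after test.* It can be read as an aim of the programme, with objective 8 supplying the test.

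ANOVA is also unqualified and could mean the repeated-measures form, although Tukey and the parallel with Kruskal-Wallis point to one-way. The Annex II remark on early recovery is teaching material about function, so it does not establish how BDI scores evolve untreated. The lack of a control in a within-arm comparison does not depend on it.

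None of this supplies a method for change within patients.

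**Conclusion.** The mismatch is real but limited. The design measures the same patients repeatedly, and the analysis section offers no test suited to that. Any comparison over time run with the named tests would be strongly conservative: a true size of about 0.6% to 0.03% for ρ between 0.5 and 0.7 (1.9% at 0.3), with roughly half or less of the attainable power for a 0.4 SD change at ρ of 0.5 to 0.7. These sizes rest on assumed correlations and changes, and on normal scores with equal variances.

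The harm is missed change and unused information, not a demonstrated risk of false claims of benefit. Single-visit arm comparisons and the sample size of 70 are unaffected. Objective 7 needs attention for a second reason: a within-arm fall cannot separate education from spontaneous recovery, whatever test is used.

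**What to change.** Amend the Statistical analysis plan section as follows.

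1. For each score, compare the arms at 3 and 6 months with adjustment for the admission score. Use either a mixed model with arm, visit, arm-by-visit, admission score and a patient random effect, or ANCOVA at each visit. Report the arm difference with a 95% CI at each visit.
2. Fix the admission score as the single baseline, since Annex III records the BDI and MMSE at several in-hospital moments.
3. If rank tests are kept, which is reasonable for bounded scores in arms of 35, use signed-rank or Friedman within patients. Use Mann-Whitney only between arms, at one visit or on per-patient change.
4. Keep the relative risk, but tie it to one dichotomised outcome at one named visit. That also fits the two-proportion basis of the sample size.
5. Assess objective 7 by the between-arm difference in change.
6. State that repeated scores from one patient will not be entered as independent observations.

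The cost is about a paragraph of text and a little more analysis work. No extra patients, visits or data are needed.

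### The intervention effect is fixed as a relative risk with no event attached, although the outcomes are scores, and the plan does not say whether the RR or the score comparison decides

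*Protocol*

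**What the plan says.** **Effect measure.** The Statistical analysis plan section of the protocol states: "The effect of the intervention will be determined using relative risk (RR"). It attaches no event, cut-off, variable or visit.

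**Outcomes.** Under Primary and secondary variables, the five dependent variables are the MMSE, BDI, Barthel, NIHSS and quality-of-life scales. Two of the entries read "Assessment of depression symptomatology by scoring on the Beck questionnaire (BDI") and "Assessment of quality of life by scoring on the European Quality of Life Scale". The general objective concerns quality of life and depression symptoms. Specific objective 8 is "To compare the level of depression symptoms in patients who have suffered an ischemic stroke who received health education with those who did not".

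**Score tests.** The same analysis section plans means and SDs, and then tests for quantitative variables. For non-normal data this is Kruskal-Wallis, "while the differences between pairs will be analyzed using the Mann-Whitney U test"; for normal data it is ANOVA with Tukey and Bonferroni. These are presented as general comparisons and are not called the analysis of the intervention effect.

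**Possible cut.** Annex I describes a BDI of 14 or more as clinically significant depression, next to four severity bands. It does not mention the RR. The quality-of-life scale has no cut.

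**Timing.** Description of the intervention plans "collection of the variables to be studied upon admission" and reassessment 3 and 6 months after the intervention.

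**Sample size.** Justification of the sample size uses a two-proportion formula with "P2 (frequency of exposure between controls) = 0.4", an odds ratio of 4 and 1:1 allocation, giving 35 per arm.

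**The concern.** A relative risk cannot be computed from a score until an event is defined. As written, the one measure assigned to the intervention effect is undefined for both outcomes in the study hypothesis. The score tests can be computed on those outcomes and answer objective 8 directly, but the effect is not assigned to them.

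Three things follow:

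- The same scores receive two analyses, with no rule for which one counts if they disagree.
- The size of the RR depends on a cut that has not been chosen.
- If the RR carries the conclusion, a score is reduced to above or below a line. That discards information in a trial of 70 patients.

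This goes beyond detail that a separate analysis plan would supply, because the protocol itself names the effect measure.

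**Working it through.** **1. Reproduce the protocol's sample size.** Inputs: p2 = 0.4, OR = 4, 1:1 allocation, two-sided 0.05. Power is not stated, so 80% is assumed.

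- p1 = OR·p2 / (1 − p2 + OR·p2) = 1.6 / 2.2 = 0.727; mean proportion 0.564.
- n = [1.96·√(2·0.564·0.436) + 0.842·√(0.198 + 0.240)]² / 0.327² = (1.375 + 0.557)² / 0.107 = 34.8, so 35 per arm.

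The stated 35 is reproduced. The RR is therefore in keeping with how the trial was sized, although the proportion is called an exposure and no outcome event is named there either.

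**2. Power of the event comparison against the score comparison.** The documents give no SD, so this step rests on assumptions: 35 per arm, two-sided 0.05, and a shift of 0.68 SD (where a t-test has 80% power). With normal scores and 40% of controls above the cut, the intervention proportion is 1 − Φ(0.253 + 0.68) = 0.175.

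| Scenario | Chi-square | Mann-Whitney | t-test |
|---|---|---|---|
| Normal scores, 40% vs 17.5% | 55% | 78% | 80% |
| Skewed BDI limited to 0-63, 40% vs 17.5% at or above 14 | 55-56% | about 60-70% | 72-75% |
| Normal scores, OR 4 as written, 40% vs 72.7% | 79% | 93% | 94% |
| Normal scores, OR 4 read as a reduction, 40% vs 14.3% | 69% | 91% | 92% |

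Chi-square power is by exact binomial enumeration and normal t-test power by the noncentral t distribution; the rest is simulated. The skewed case uses gamma-distributed scores with shape 1 to 3, rounded and limited to the BDI range.

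**3. How often the two analyses disagree.** In the first scenario, the score test is significant and chi-square is not in 25-27% of trials. The reverse occurs in about 2%. If there were no effect and either test counted as success, false positives would be 7.3-7.7%. The protocol does not state such a rule; the figure shows what leaving precedence open could allow.

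**4. Dependence of the RR on the cut.** With the same 0.68 SD shift in normal scores:

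- 40% of controls above the cut: RR = 0.175 / 0.40 = 0.44.
- 20% of controls above the cut: RR = [1 − Φ(0.842 + 0.68)] / 0.20 = 0.064 / 0.20 = 0.32.

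**5. Precision of each measure.**

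- RR, with counts of 6/35 vs 14/35: 0.43. SE of log RR = √(1/6 − 1/35 + 1/14 − 1/35) = 0.425, so the 95% CI is 0.19 to 0.99.
- Mean difference, unadjusted: half-width 1.995·√(2/35) = 0.48 SD.
- Mean difference, adjusted for an admission score correlated 0.5 with follow-up: 1.996·√(2/35)·√0.75 = 0.41 SD.
- Adjustment raises power at 0.68 SD from 80% to 82%, 84% or 90% at correlations of 0.2, 0.3 or 0.5. This is a gain in efficiency; it does not correct a bias.

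**The case against.** The best defence is that the RR matches the design. The trial was sized on two proportions, Annex I offers a natural event in BDI of 14 or more, and at the odds ratio as written the event comparison has 79% power, close to a conventional 80%. Event and visit are details that an analysis plan could add. This stands in part: the RR is legitimate as a secondary measure. It also suits the clinical events in objective 5, which begins "Assess and compare the risk of bronchoaspiration, the presence of pressure ulcers". But Annex I does not choose the event, quality of life has no cut, and the protocol's stated objective is the level of symptoms.

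The power gap also depends on the scenario. The 25-point contrast needs normal scores and a shift chosen to give the t-test 80% power. For skewed BDI scores the protocol would use Mann-Whitney, and the gain is then only about 6 to 14 points.

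Two stronger readings are tempting, and the text does not support them:

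- A reader might infer that the score tests give no effect estimate. Means and SDs are planned, and Tukey or Bonferroni procedures can output mean differences. What is absent is a planned between-arm difference with a confidence interval.
- A reader might infer that the score tests exclude the admission score and the follow-up visits. The analysis section is silent on visits and covariates, and silence is not exclusion.

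**Conclusion.** The point holds as a should-fix. The mismatch between a relative risk and score outcomes, and the absence of a rule on which analysis decides, can be read directly from the protocol and need no assumption.

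The size does rest on assumptions. For 40% vs 17.5% above the cut, the event comparison has about 55% power, against 78-80% for score tests on normal data and about 60-75% on skewed BDI data. For the odds ratio as written it has 79%, against 93-94% for score tests on normal data. The headline RR could be 0.44 or 0.32 for the same shift.

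It would go too far to say that the trial will miss a benefit. Objective 8 calls for the comparison of depression levels, and a suitable test is planned. The risk is that this comparison is not the one that determines the effect. Nor is the RR invalid; it is incompletely defined and less informative as the main measure.

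**What to change.** In the Statistical analysis plan section, replace the RR sentence with text along these lines: the intervention effect is the between-arm difference in mean BDI score, with 95% CI, at one named follow-up visit, estimated by ANCOVA adjusted for the admission BDI score, with Mann-Whitney as the check for skewed scores. The sponsor chooses between 3 and 6 months.

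Analyse quality of life in the same way once the instrument is settled. Annex I describes the five-level EQ-5D with a visual analogue scale, while the form in Annex III has three levels per item and shows no such scale. The version and the score to be analysed must be named first.

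Keep the RR as secondary for a defined event (for example BDI of 14 or more at the named visit) and for the binary clinical events in objective 5.

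**Cost.** Rewording and slightly more analysis work, plus 3- and 6-month fields in the Annex III data notebook, whose header shows none. Justification of the sample size should note that 35 per arm was derived for two proportions. The precision of the score analysis, about ±0.48 SD unadjusted before dropout and any clustering by education group, then rests on an SD that the documents do not give; the sponsor must supply one to express it in points. No extra visits or patients are needed, because the admission, 3- and 6-month assessments are already planned.
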